6.12.6 Febrile Episodes

Fever (defined in this study as any temperature $>38.3^{\circ}\text{C}$; $\geq 101.0^{\circ}\text{F}$) commonly occurs in up to 70% of patients following aSAH and may contribute to short and long-term morbidity. Fever without concomitant infection has been implicated as a cause of worsened neurological function and cognitive disability. **Guidelines from the Neurocritical Care Society and American Heart Association recommend maintaining normothermia after aSAH.** Our hypothesis that modulating the inflammatory response will have the potential to reduce the incidence of delayed neurological deficits and cognitive dysfunction in aSAH is intimately related to clinical signs of inflammation such as fever. Blood within the cerebrospinal fluid can induce fever by the release of inflammatory cytokines in the absence of true infection. In addition, aSAH patients are predisposed to hospital-acquired infection such as urinary

tract infection, ventilator associated pneumonia (VAP), and ventriculitis associated with external ventricular drainage catheters. Other medications commonly used in aSAH patients such as phenytoin can cause drug fevers. Increasing fever burden is a long-term predictor of poor functional and cognitive recovery following aSAH. As a result, neurocritical care specialists now promote aggressive fever control in aSAH patients. In fact, a clinical trial is in development to evaluate normothermia in aSAH (NASH) and is focusing on pharmacological therapy with intravenous ibuprofen and other aggressive fever reduction methods.

It is possible that UFH will modulate the inflammatory response to the point of reducing fever burden preferentially in the LDIVH arm. This may lead to improved clinical functional measures such as perseveration of cognitive function. It is also possible that a significant muting of the inflammatory response will limit the body's natural inflammatory mechanism to fend off infectious insults resulting in the possibility of unintended infectious complications which if not recognized early in their course (i.e., no heralding fever, elevated serum WBC count) could become more difficult to treat with antibiotics. However, this theoretical risk of increased infections as a result of improved fever control was not borne out in a study undertaken at Columbia University when comparing conventional fever control methods to aggressive fever control methods (Badjatia N et al. *Neurosurgery* 2010;66(4):696-700) and was not identified in more than 100 post-craniotomy patients treated with the LDIVH protocol.

This study will monitor fever episodes and overall daily fever burden. It will also track all infectious events and consider them adverse events (AEs) as well as track any anti-microbial therapies. The following recommendations are made to merge the goals of this study with the Neurocritical Care Society's Consensus recommendations:

- **The cause of fevers should be investigated and treated aggressively per the SOC at each clinical site based on guidelines set forth by the Society of Critical Care Medicine (SCCM) and the Neurocritical Care Society** which may include antimicrobials (for proven or suspected infections), other pharmacological agents and utilization of temperature modulation devices (TMDs).
- **The overall efficacy of most antipyretics is low and we prefer avoidance of acetaminophen and / or ibuprofen for fever control unless required per the SOC at the institution as these medications could confound our study results.** If these medications are deemed necessary per the SOC at the institution, then the dose, duration, and timing of the medications will be recorded in the EDC system and **statistical analysis will be done to determine if there is any confounding influence of these medications on the study results.**
- **Surface cooling or intravascular devices are generally more effective than antipyretics and could be considered for fever control when antipyretics are not utilized. Use of these devices should be accompanied by monitoring for skin injury and venous thrombosis.**

- **Patients should be monitored and treated for shivering.**

Fever will be defined in this study as core body temperature of > 38.3° C (≥ 101° F). Core body temperature measurements are preferred and should be measured using one of the following devices when possible: pulmonary artery thermistor, urinary bladder catheter thermistor (Foley), esophageal probe, rectal probe. Pulmonary artery catheters are currently uncommonly used in the management of aSAH patients within the intensive care setting, however if the catheter is already being utilized for other purposes in the study subject, then core body temperature may be measured from this catheter as this is considered the gold-standard for core body temperature measurement.

The most common core body temperature measurement option for aSAH patients with limited invasiveness would be the urinary bladder catheter thermistor and this is the preferred method for this study due to the high accuracy of these measurements. Most aSAH patients need critical input and output measurements requiring urinary bladder catheter placement in the critical care setting. In addition, the tendency to give generous intravenous fluid volumes to these patients tends to increase the utilization of urinary bladder catheters to avoid hourly trips to the toilet or soiling of bed linens. Yet in recent years there has been a trend towards early urinary bladder catheter removal to prevent hospital acquired urinary tract infections. Therefore, while core body temperature measurements utilizing the urinary bladder catheter thermistors would be an ideal option in aSAH subjects enrolled in this study, the urinary bladder catheters should be removed when appropriate based on the SOC at each clinical site and should not be continued only for temperature measurements for this study if this would fall outside of the site's SOC.

Esophageal temperature probes in the lower 1/3 of the esophagus are reasonable core body temperature measuring devices and are acceptable for temperature measurements in this study. However, these are most common in intubated patients, and we expect very few of our enrolled patients to have endotracheal intubation during study drug infusion. On awake, non-intubated patients esophageal temperature probes can still be utilized, but may be uncomfortable to patients.

Newer central venous catheter temperature probes (Alsius/Zoll) may also be utilized. Rectal probes may also be used but tend to be slightly less accurate than urinary and esophageal probes. **If none of these probes are available, then oral temperature probes placed in the sublingual space are acceptable** but proper attention should be given to recent eating, drinking, mouth breathing and proper probe placement to improve accuracy.

Infrared ear thermometry tends to be less accurate and is not recommended for this study. Temporal artery thermometers, skin surface thermometers and axillary thermometers are not allowed for purposes of temperature data collection in this study.

Temperature measurements will be recorded into the medical record while the patient is in the intensive care unit according to each site's SOC, but at least every 4 hours. If there is more than one measurement obtained within a given hour, then the highest measurement obtained during that hour will be utilized as temperature data for this study. The method of temperature monitoring should be recorded.

Temperature logs will be collected for each subject. Missing temperature time points will be assumed to equal the most recent previously recorded temperature. A total daily fever burden will be calculated for the duration of the study drug infusion (Daily Fever Burden = Sum of hourly fever burden over 24 hours; Hourly Fever Burden = Any hourly temperature recording $> 37.0^{\circ}\text{C}$ minus 37°C ; thus hourly temperature readings of 37°C or less will result in a "0, zero" fever burden for that hour).

If the patient is not in the ICU and is having temperature measurements every 4 hours, then the 4-hour temperature burden will be calculated as temperature measured during that 4 hours window (or highest measurement if more than one measure) minus 37°C x 4. The Daily fever burden will then be the sum of the six 4-hour temperature burden calculations.

In addition, the T_{max} per 24-hour period will be documented in the study CRF/Database as well as the number of temperature values recorded as a fever ($>38.3^{\circ}\text{C}$) per 24 hour period. **For the purposes of this study, a day will run from 7 AM until 6:59 AM the following morning.**

Daily T_{max} , Daily Fever Burden, and # of fevers per day will be evaluated as an outcome measure on enrollment day # 2, 4, 6, and 10 to determine any correlation between fever and individual inflammatory biomarker levels and neurological assessments and MoCA scoring at each time point (# 6 and 10). Also, the mean of each subject's average hospitalization daily fever burden (up to 21 days) will be analyzed in relation to the mean of the biomarker levels summed over enrollment days #2, 4, 6, and 10 per study treatment group. Finally, presence of any temperature $> 38.3^{\circ}\text{C}$ and multiple febrile episodes (>2) for a study subjects will be noted and compared between treatment groups as an analysis of categorical proportions.

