1.2.2 Secondary Objectives

1. Measure the correlation between blood / CSF levels of inflammatory biomarkers (e.g. hsCRP, IL-6) and cognitive function (MoCA).
2. Demonstrate a reduction in blood / CSF levels of inflammatory biomarkers (e.g. hsCRP, IL-6) in the LDIVH treated subjects compared to controls.
3. Demonstrate a reduction in cerebral vasospasm in the LDIVH treated subjects compared to controls by measuring the proportion of patients in each group who:
 - i. Demonstrate moderately severe or severe angiographic vasospasm by CTA or DSA obtained within the prime vasospasm window
 - ii. Demonstrate moderately severe or severe vasospasm on transcranial Dopplers (TCDs)
 - iii. Demonstrate vasospasm related CT infarctions
4. Demonstrate a reduction in “Delayed Cerebral Ischemia” as defined by the Neurocritical Care Society:
 - i. Symptoms of neurological deterioration (e.g., hemiparesis, aphasia, altered consciousness) presumed to be related to ischemia
 - ii. Symptoms persist for more than one hour
 - iii. Symptoms cannot be explained by other physiological abnormalities
5. Demonstrate a reduction in the need for “rescue therapy” for delayed cerebral ischemia and / or symptomatic cerebral vasospasm
6. Demonstrate a difference between the LDIVH treated subjects and controls in the proportion of patients in each group who:
 - i. Have any fever (Temperature $\geq 38.3^{\circ}\text{C}$ / 101.0°F)
 - ii. Have multiple fevers (≥ 3 fever episodes)
7. Demonstrate a significant difference in “fever burden” between LDIVH treated subjects and control subjects
8. Demonstrate a difference between LDIVH treated subjects and controls in mean Daily Fever Burden during the LDIVH infusion.

9. Demonstrate better clinical outcomes in the LDIVH treated subjects compared to controls with one of the following measures:
 - i. mRS at 90 days and 1-year (Ordinal Regression Analysis)
 - ii. Barthel Index at 90 days
 - iii. Center for Epidemiologic Studies Depression Scale (CES-D) at 90 days and 1-year
 - iv. QOLIBRI-OS at 90 days and 1-year
 - v. Lawton IADLs at 90 days
 - vi. Trail Making Test Parts A&B at 90 days
 - vii. Return to Work Status at 90 days and 1-year
 - viii. MoCA at 1-year
10. Perform Pre-specified Subgroup Analysis of Outcome measures for LDVIH and Control groups using the following subgroup designations:
 - i. Sex (Male versus Female)
 - ii. Admission CT Hijdra Sum Score (<23 versus ≥ 23)

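### Daily Fever Burden has a zero floor in the hourly rule but none in the ward 4-hour rule, so ward readings below 37°C subtract from real fever

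*Protocol*

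**What the plan says.** Protocol section 6.12.6 gives a general rule: "Daily Fever Burden = Sum of hourly fever burden over 24 hours". Each hour contributes its excess over 37°C, and the clause beginning "readings of 37°C or less will result in a" goes on to assign zero for that hour. If an hour has several readings, "then the highest measurement obtained during that hour will be utilized as temperature data for this study". ICU readings are taken "according to each site's SOC, but at least every 4 hours", and gaps are filled: "Missing temperature time points will be assumed to equal the most recent previously recorded temperature".

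The next paragraph covers patients outside the ICU who are measured every 4 hours. The window's temperature, or the highest if there is more than one, has 37°C subtracted and is multiplied by 4. "The Daily fever burden will then be the sum of the six 4-hour temperature burden calculations". The zero clause is not repeated, and the formula has no brackets.

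The variable is used in several places:
- Section 1.2.2, objective 7 concerns fever burden, and objective 8 reads: "Demonstrate a difference between LDIVH treated subjects and controls in mean Daily Fever Burden during the LDIVH infusion".
- The synopsis lists Mean Daily Fever Burden among the exploratory outcome analyses.
- Section 6.12.6 relates daily burden on days 2, 4, 6 and 10 to biomarkers and neurological assessments, and to MoCA on days 6 and 10. It also relates each subject's average daily burden, over up to 21 hospital days, to biomarker levels.
- Section 6.8 allows the infusion to run in or out of the ICU.

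**The concern.** A fever burden should measure exposure above a threshold, and the hourly rule does this. The ward rule as written measures the net deviation from 37°C instead. A normal or cool reading then earns negative burden, which is set against genuine fever elsewhere in the same day. The same chart can therefore score differently depending on where the bed is.

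Patients move between ICU and ward during the period analysed, so a patient's average can combine two quantities that are not on the same scale. At best this adds noise to the between-arm comparison. If ward time or measurement frequency differs by arm, part of that difference appears as a fever-burden difference. If ward location goes with better neurological condition, the lower ward scores build in part of any association between fever and cognition, even with the arms perfectly balanced.

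**Working it through.** The protocol gives no numerical example of fever burden, so there is no figure to reproduce. Both rules were applied to the same 24-hour charts. The temperatures are illustrative assumptions, not trial data. Units are degree-hours.

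**Formulas from section 6.12.6**
- Hourly rule: sum over 24 hours of max(T - 37, 0).
- Ward rule as written, with the evident brackets supplied: sum over six windows of 4 x (window value - 37), no floor. Without the brackets, 38°C would give 38 - 37 x 4 = -110 for a single window, which cannot be meant.

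**1. Effect of the missing floor, one reading per window**
- Constant 36.6°C. Hourly: 0. Ward: 6 x 4 x (-0.4) = -9.6.
- One window at 38.6°C, five at 36.6°C. Hourly: 4 x 1.6 = +6.4. Ward: 6.4 + 5 x 4 x (-0.4) = 6.4 - 8.0 = -1.6. A day with a reading above the protocol's own fever threshold of 38.3°C scores below zero.
- Readings 36.5, 36.8, 37.2, 38.5, 38.0, 36.7. Hourly, carried forward: 4 x (0.2 + 1.5 + 1.0) = 10.8. Ward: 4 x (-0.5 - 0.2 + 0.2 + 1.5 + 1.0 - 0.3) = 4 x 1.7 = 6.8.

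The average daily shortfall on the ward is 24 x E[max(0, 37 - T)]. With T assumed normal and SD 0.5°C, it is 4.8 for a mean of 37.0°C, 2.8 for 37.2°C and 1.4 for 37.4°C.

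**2. Where the rules agree**
- Constant 38.0°C: 24.0 under both.
- Readings 37.1, 37.5, 38.0, 38.5, 38.0, 37.2, one per window: 4 x (0.1 + 0.5 + 1.0 + 1.5 + 1.0 + 0.2) = 17.2 under both.

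**3. With a floor added to the ward rule**
- Constant 36.6°C becomes 0.
- The 10.8 versus 6.8 example becomes 10.8 under both.

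With one reading at the start of each window, carried forward, the floored ward rule and the hourly rule are the same calculation.

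**4. What the floor does not repair: several readings in one ward window**
- Hourly 37.2, 37.6, 38.0, 38.4 in each window. Hourly: 6 x (0.2 + 0.6 + 1.0 + 1.4) = 19.2. Ward: 6 x 4 x 1.4 = 33.6.
- A one-hour peak of 39.0°C in each window, otherwise 37.0°C. Hourly: 6 x 2.0 = 12.0. Ward: 6 x 4 x 2.0 = 48.0.

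These two charts assume hourly readings on the ward and are extreme cases.

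**The case against.** The strongest reply is that the floor was simply left out in drafting. The preceding paragraph counts only readings above 37°C, and the next adapts that idea to 4-hourly data. The ward formula already has to be read with brackets that it lacks, so a sensible programmer might supply the floor as well. That is plausible, but the text states a formula, the formula gives negative burdens, and two programmers could derive different datasets from it.

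Other parts of the reply stand in full. The ICU requires readings only every 4 hours, with carry-forward, so an ICU day may rest on six readings just as a ward day does. With one reading per window, all at or above 37°C, the rules agree; a reader might infer that identical temperatures always score differently, and that is not so.

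A reader might also infer that the maximum-times-4 step inflates ward burden generally. The ward rule applies to patients measured every 4 hours, normally one reading per window, and the maximum is then that reading. The inflation arises only in windows with extra readings, which the text foresees but does not treat as usual.

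Finally, a reader might infer that the comparison between arms is biased. The protocol gives no evidence of unequal ICU time: section 6.8 says the infusion should not hold up transfer from the ICU, and section 6.18 expects no extra ICU days from taking part. Bedside care is unblinded (section 5.4) and a complication could change location, so equal ICU time is not guaranteed, but a difference is not shown either.

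**Conclusion.** The point holds as an inconsistency in a stated formula: the ward rule is wrong as written, not merely short of detail. For days with readings below 37°C the error reaches 9.6 degree-hours in the constant 36.6°C example, and it can turn a day with fever negative. Under the assumed normal temperatures (mean 37.0 to 37.4°C, SD 0.5°C), it lowers ward burden by 1.4 to 4.8 degree-hours per day on average.

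The certain consequence of mixing the two scales is noise in the fever-burden comparison and in the correlations with biomarkers and MoCA. Bias is conditional on ward time or measurement frequency differing by arm or with outcome.

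The reach is limited. Fever burden is a secondary objective that the synopsis lists as exploratory, and it is not part of the definition of study success. The primary MoCA and bleeding endpoints are untouched.

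**What to change.** In section 6.12.6, state the 4-hour burden as 4 x max(0, temperature - 37), with the brackets and the floor written out. With one reading per window carried forward, this equals the hourly rule, so ICU and ward days are then on one scale.

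Where a ward window has more than one reading, apply the hourly rule with carry-forward instead of the maximum times 4. A common 4-hour grid for ICU and ward can be a sensitivity analysis; it need not replace the hourly data.

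The cost is a short text change and some programming. Temperature logs are already collected for every subject, and no new data or change to patient care is involved.

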Peak and Overall Plasma and CSF levels of hsCRP at enrollment and, infusion days #2, 4, 6, and 10 compared between groups.

-SECONDARY CLINICAL EFFECT ENDPOINTS

Trail Making Test Parts A&B at 90 (± 10) days post enrollment.

MoCA at 1-year (± 30 days)

Center for Epidemiologic Studies Depression Scale (CES-D) at 90 (± 10) days post enrollment

Return to work status between groups at 90 (± 10) days

SECONDARY EXPLORATORY PRESPECIFIED BIOMARKER OUTCOMES

Plasma and CSF levels of IL-6, TNF- α , P-Selectin, sICAM-1, HMGB-1, MRP8/14 plasma levels at enrollment and infusion day #2, 4, 6, and 10

ADDITIONAL PRE-SPECIFIED

Rate of MoCA ≤ 20 between groups at the 90-day follow-up visit.

**EXPLORATORY
OUTCOME ANALYSES**

In-hospital incidence of any fever ($> 38.3^{\circ} \text{C}$; $\geq 101.0^{\circ} \text{F}$), Incidence of multiple fever episodes (≥ 3), and Mean Daily Fever Burden.

GCS and NIHSS at enrollment and infusion days # 2,4,6,10, discharge and 90 (± 10) days

MoCA at post-enrollment day #1, 6 and 10

Correlation analysis between MoCA scores and inflammatory biomarker levels with and without adjusting for hemorrhage burden (Hijdra Sum Score).

Incidence of moderate and severe Radiographic Cerebral Vasospasm based on a CTA, MRA, or Catheter DSA obtained between PBD # 6-12 as determined by an independent and blinded core imaging lab.

Incidence of TCD criteria for significant vasospasm (velocities $>200 \text{ cm/s}$ and / or MCA / ICA (Lindgaard) ratio >6)

Incidence of TCD criteria for absence of vasospasm (velocities $<120 \text{ cm/s}$)

Incidence of clinical vasospasm requiring rescue therapy (eg, pressors, endovascular treatment)

Incidence of "Delayed Cerebral Ischemia" defined as:

- Symptoms of neurological deterioration (e.g. hemiparesis, aphasia, decreased level of consciousness)
- Symptoms last for more than an hour
- Symptoms are not explained by other physiological processes (e.g., hydrocephalus, hypotension)

CT or MRI evidence of Vasospasm Related Cerebral Infarction on post-infusion (discharge) imaging as scored by an independent and blinded core imaging lab

Global outcome as measured between group ordinal regression analysis of the modified Rankin Scale score at 90-days and 1-year.
Return to work status between groups at 1-year.
Lawton IADLs at 90 (± 10) days
QOLIBRI-OS at 90 (± 10) days and 1-year.
Checklist Individual Strength-subscale Fatigue (CIS-f) at 90 (± 10) days
Barthel Index at 90 (± 10) days and 1-year

**INVESTIGATIONAL

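### The only fever count the protocol defines is a number of readings, which depends on charting frequency, and the fever threshold differs between sections

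*Protocol*

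**What the plan says.** **The count.** Section 6.12.6 opens with "Fever (defined in this study as any temperature" over the threshold, so a single reading is enough and no duration is required. Besides the daily maximum, the section puts on the case report form the "number of temperature values recorded as a fever" in each 24-hour period. It then says that the number "of fevers per day will be evaluated as an outcome measure on enrollment day # 2, 4, 6, and 10", to be correlated with biomarkers, neurological assessments and MoCA.

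**The episode outcome.** The same paragraph says that "multiple febrile episodes (>2) for a study subjects will be noted and compared between treatment groups". The synopsis (1.1) lists "Incidence of multiple fever episodes (≥ 3") among the exploratory analyses. Section 1.2.2, item 6, makes it a secondary objective: "Have multiple fevers (≥ 3 fever episodes"). The protocol does not say what separates one episode from the next.

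**Charting.** ICU temperatures are recorded "according to each site's SOC, but at least every 4 hours", with at most one value (the highest) used per hour. Four-hourly charting is provided for outside the ICU. For those patients fever burden is multiplied by 4; nothing equivalent is given for the fever count. Missing time points take the last recorded temperature. Temperature logs are collected for every patient.

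**The threshold.** Section 1.2.2 sets fever at or above 38.3°C / 101.0°F. Sections 1.1 and 6.12.6 set it strictly above 38.3°C, paired with at or above 101°F, and the last paragraphs of 6.12.6 give only the strict Celsius form.

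**The concern.** A count of febrile readings measures hours of fever multiplied by charting rate, not the number of fevers. Two patients with the same temperature course get different counts if one is charted hourly and the other four-hourly, and one patient's count can change on transfer from ICU to ward. Section 6.12.6 recognises this for fever burden, where it rescales, but leaves the count unadjusted.

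The daily number of fevers is to be correlated with biomarkers and MoCA, so charting habits enter one side of that correlation. If the count is also used for the episode outcome, the cut of three no longer separates recurrent fever from one long fever. The threshold conflict affects the any-fever outcome as well, because a charted 38.3°C is a fever in one section and not in the others.

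**Working it through.** The plan states no figure for these outcomes, so there is none to reproduce. The check counts readings.

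**1. One continuous fever.** Let the fever last L hours, with readings every s hours and the first reading falling at random. The number of febrile readings is then the whole part of L/s, plus one more with probability equal to the fractional part.

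- L = 3, hourly: 3/1 = 3 readings, which meets the cut of three.
- L = 3, four-hourly: 3/4 = 0.75, so 1 reading (75%) or 0 (25%).
- L = 6, four-hourly: 1.5, so 1 or 2 readings, equally likely.
- L = 9, four-hourly: 2.25, so 2 readings (75%) or 3 (25%).
- L = 12, four-hourly: 3 readings.

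Four-hourly, a single fever must last more than 8 hours to be able to reach three readings. Hourly, 3 hours is enough.

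**2. Three separate 3-hour fevers, four-hourly.** Reaching three readings requires all three to be caught: 0.75 × 0.75 × 0.75 = 0.42. A truly recurrent pattern is missed 58% of the time, while one fever charted hourly qualifies every time.

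**3. With carry-forward.** If each four-hourly value fills the next three hourly slots and those slots are counted, the 3-hour fever gives 4 (75%) or 0 (25%) rather than 1 or 0. The protocol does not say whether this applies to the count.

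**4. A population illustration, conditional on the count feeding the episode outcome.** Section 6.12.6 says that fever "commonly occurs in up to 70% of patients following aSAH". Assume Poisson episodes with mean 1.2: at least one in 1 − e^(−1.2) = 70%, and three or more in 1 − e^(−1.2) × (1 + 1.2 + 0.72) = 12%. Assume gamma durations (shape 2) and vary the mean. The simulated share with three or more recorded febrile readings is:

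| Mean duration | Hourly | Four-hourly |
|---|---|---|
| 2 h | 38% | 3% |
| 3 h | 50% | 9% |
| 5 h | 60% | 23% |
| 8 h | 65% | 38% |

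Repeat runs differ by about a percentage point. At 5 h with carry-forward counted, four-hourly charting gives about 61%. The two schemes then agree, but at about five times the true 12%.

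**5. The threshold.** 38.3 × 9/5 + 32 = 100.94°F, and (101.0 − 32) × 5/9 = 38.33°C. A reading of 101.0°F is therefore a fever under every section, but entered to one decimal as 38.3°C it fails the strict rule in 1.1 and 6.12.6 and passes the rule in 1.2.2.

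**The case against.** A reader might infer that the episode outcome is computed from the count of readings. The protocol does not say so. The two appear in neighbouring paragraphs, but the logs are also collected and episodes could be derived from them. An undefined episode alone is detail that an analysis plan may supply. This objection stands, so every statement here about the episode outcome is conditional.

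The carry-forward rule could remove the contrast between hourly and four-hourly charting. That also stands as a possibility. It does not rescue the count, which would still track hours of fever.

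A reader might also infer a biased comparison between arms. The document does not show one. Randomization balances site habits in expectation, section 6.4 plans statistical control for site, and section 6.8 says that the infusion should not delay leaving the ICU. Treating staff are unblinded (5.4), so charting or ICU stay could differ by arm, but nothing shows that they do. In addition, the daily number of fevers is planned for correlations and is not stated as a between-arm comparison.

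Finally, daily fever burden, which is rescaled, also serves the fever hypothesis, and the threshold conflict concerns only readings at 38.3°C. Both are fair points and keep the matter small.

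**Conclusion.** The point holds in a limited form. The one fever count that is defined depends on charting frequency, section 6.12.6 corrects fever burden for this but not the count, and the role of carry-forward in the count is left open. Separately, the threshold in 1.2.2 contradicts 1.1 and 6.12.6.

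For recorded values, the result of 3 readings against 1 or 0 for a 3-hour fever rests only on a continuous fever and a random first reading. The population shares rest on assumed episode numbers and durations and apply only if the count is used for episodes. They show how far such a count could sit from the true share; they do not estimate an effect on the difference between arms.

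Severity is low. The fever outcomes are exploratory in the synopsis and secondary in 1.2.2. The primary endpoints, sample size and definition of study success do not depend on them.

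**What to change.** - Derive fever counts and episodes from the temperature logs on a common 4-hour grid for every patient, in the ICU or on the ward, taking the highest value per block. Join consecutive febrile blocks into one episode; a new episode needs at least one intervening block without fever.
- State that a carried-forward value does not create a febrile reading.
- Use one threshold in 1.1, 1.2.2 and 6.12.6, and convert °F to °C before applying it, without rounding first.
- Settle this before the unblinded final analysis.

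The cost is a programming rule and short edits in three sections, with no new data collection. There are two downsides. Fevers close together are merged. Hourly charting will still detect somewhat more episodes, because a block then holds up to four readings instead of one. Under the same assumptions, the share with three or more episodes becomes about 10% hourly against 6% four-hourly at a 5-hour mean, 8 to 9% against 2% at 2 hours, and 10% against 8% at 8 hours; the true share is 12%. A sensitivity analysis using one reading per block, or adjusting for site, would show whether the remaining gap matters.
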